6.1.8 Dose Adjustments/Modifications/Delays

As stated in Section 6.1.7, dose changes will be made according to subjects' responses. Any subjects that experience moderate side effects will have their dose lowered to the previous dose for the remainder of that study phase. If a subject is found to have urine electrolyte (sodium) or osmolality abnormalities during study visits, study medication will be discontinued and the subject will have to withdraw from the study.

6.1.9 Duration of Therapy

The study consists of 3 phases:

- 1. 1 week baseline period during which no study medication will be administered.
- 9 week non-blinded phase during which all subjects receive oxytocin nasal spray (30 45 IU four times/day)
- 3. 6 week "double-blind" phase during which half the subjects receive oxytocin nasal spray (up to 45 IU four times/day) or the placebo nasal spray.

6.1.10 Tracking of Dose

Subjects will be asked to bring their study medication bottles in to each office study visit, every other week. They will also be asked to complete a daily tinnitus severity log that will also ask if they have taken each dose that day.

6.2 Study Agent Accountability Procedures

After the compounding pharmacy prepares and delivers the active drug and placebo, the study coordinator will have access to the secure refrigerator where study drug is stored. At Visits 3, 5, 7, and 9, she will distribute the study agent (oxytocin nasal spray) to each participant. The participants will receive only enough of the study agent for the next 2 weeks of the study. They will have to return to the office at weeks 11 and 13 to receive study drug or placebo for the double blind phase of the study.

Regular study drug reconciliation will be performed to document drug assigned, drug consumed, and drug remaining. This reconciliation will be logged on a drug accountability log, and signed and dated by the study team.

Subjects will receive a phone call from the study coordinator to discuss the subject's experience using the study drug the prior week. Subjects will also have to complete a daily log noting the severity of their tinnitus for that day and the time they took their medication. Study staff will review this information at each visit, every other week.

7 Study Procedures and Schedule

7.1 Study Procedures/Evaluations

Patients will come to the Preston Robert Tisch Center for Men's Health for study visits every 2 weeks and be administered the VAS and THI/CGI scales by the research coordinator or principal investigator. The screening visit will be the most comprehensive and include obtaining informed consent, a physical exam with vital signs, laboratory studies, questionnaires, an ECG, and review of medical and medication history

to confirm all inclusion criteria are met and that there are no exclusion criteria present. During these visits they will have urine testing for sodium and osmolality. Every other week, they will receive a phone call from study staff to discuss their experience using the study drug and monitor for any adverse effects. They will complete the Tinnitus Functional Index questionnaire over the phone as well. When the subjects come in for their study visit, 4 weeks after the baseline period, they will receive enough study medication for the rest of the study, to allow for randomization to placebo or active drug at that time.

7.1.1 Study Specific Procedures

Visit Details

Visit	Visit Type	Procedures	Labs	Questionnaires	
Screening (Week 0)	Office visit	Obtain informed consent, review of medical and medication history, physical exam, vital signs, ECG	Comprehensive metabolic panel, urine electrolytes & osmolality, urine pregnancy test	Х	
Baseline (beginning of Week 1)	Phone	Review of current medications, issue daily VAS log		х	Baseline
End of Week 1	Office visit	Review of current medications, dispense active drug, review VAS log	Urine pregnancy test	х	
Week 2	Phone	Review of current medications		Х	
Week 3	Office visit	Review of current medications, study drug reconciliation, dispense active drug, study log review	Urine electrolytes & osmolality, urine pregnancy test	х	
Week 4	Phone			Х	
Week 5	Office visit	Review of current medications, study drug reconciliation, dispense active drug, study log review	Urine electrolytes & osmolality, urine pregnancy test	х	Non-Blinded
Week 6	Phone	Review of current medications		х	Phase
Week 7	Office visit	Review of current medications, study drug reconciliation, dispense active drug, study log review	Urine electrolytes & osmolality, urine pregnancy test	х	
Week 8	Phone	Review of current medications		х	
Week 9 Office visit		Review of current medications, randomize & dispense new drug, study log review	Urine electrolytes & osmolality, urine pregnancy test	Х	
Week 10	Phone	Review of current medications		Х	

Week 11	Office visit	Review of current medications, study drug reconciliation, dispense study drug, study log review	Urine electrolytes & osmolality, urine pregnancy test	х	Double Blind Phase
Week 12	Phone	Review of current medications		Х	
Week 13	Office visit	Review of current medications, study drug reconciliation, dispense study drug, study log review	Urine electrolytes & osmolality, urine pregnancy test	х	
Week 14	Phone	Review of current medications		Х	
Week 15	Office visit	Review of current medications, study drug reconciliation, study log review	Comprehensive metabolic panel, urine pregnancy test	х	

7.1.2 Clinical Laboratory Evaluations

- Blood tests: Comprehensive Metabolic Panel (CMP) at the screening visit (as abnormal values will exclude patients from the study) and final study visit
- **Urinalysis:** dipstick urinalysis, including electrolyte levels and urine concentration; if dipstick is abnormal, complete urinalysis with microscopic evaluation is required.
- **Pregnancy test**, female subjects of childbearing potential will undergo a urine pregnancy test every week that an office study visit occurs.

7.1.3 Specimen Preparation, Handling, and Storage

Labeled urine samples will be taken the same day to the Tisch Laboratory for processing. Labels will include the participant's initials, subject ID number, and date and time the sample was obtained.

7.2 Study Schedule

7.2.1 Screening

Screening Visit

- Obtain informed consent of potential participant verified by signature on written informed consent for screening form.
- Review medical history to determine eligibility based on inclusion/exclusion criteria.
- Review medication history to determine eligibility based on inclusion/exclusion criteria.
- Obtain demographic information, alcohol and tobacco use history.
- Perform medical examinations and ECG needed to determine eligibility based on inclusion/exclusion criteria.
- Draw blood for CMP to determine eligibility.
- Collect urine for electrolyte levels, urine osmolality, and pregnancy test if applicable.
- Perform questionnaires including the Tinnitus Handicap Inventory (THI), Clinical Global Impression (CGI) for baseline, and suicidality history.
 - Due to the correlation between tinnitus and suicide, the investigator will evaluate suicidality history by patient interview to be recorded in the CRF. This will be re-assessed at follow up visits as a part of the THI. If a subject reports suicidal ideation or intent at any time, they will immediately be referred to a psychiatrist or psychiatric emergency department.
- Schedule study visits for participants who are eligible and available for the duration of the study.

7.2.2 Enrollment/Baseline

Visit 2: Baseline Visit – Beginning of Week 1 (Phone Visit)

- Review of current medications.
- Administer THI and VAS questionnaires.
- Issue daily Tinnitus Severity Log/Visual Analog Scale (VAS) log by email.

7.2.3 Intermediate Visits

7.2.3.1 Visit 3: End of Week 1 (Office Visit)

- Record adverse events as reported by participant or observed by investigator.
- Record vital signs and auscultate lungs.
- Review current medications and results of VAS log.
- Perform urine pregnancy test, if applicable.
- Administer THI questionnaire.
- Provide the study medication to the participant to use four times daily for the next 2 weeks.

7.2.3.2 Visit 4: Week 2 (Phone Visit)

- Review current medications.
- Assess and record adverse events including dyspnea as reported by participant or observed by investigator.
- Record participant's adherence to treatment program.
- Administer phone Tinnitus Functional Index (TFI) questionnaire.

7.2.3.3 Visit 5: Week 3 (Office Visit)

- Record vital signs and auscultate lungs.
- Review current medications and results of VAS log.
- Collect urine for electrolyte levels and urine osmolality. Perform urine pregnancy test, if applicable.
- Administer THI and Clinical Global Impression Improvement (CGI-I) questionnaires.
- Record adverse events as reported by participant or observed by investigator.
- Study drug reconciliation and record of participant's adherence to treatment program.
- Provide the study medication to the participant to use four times daily for the next 2 weeks.

7.2.3.4 Visit 6: Week 4 (Phone Visit)

- Review current medications.
- Assess and record adverse events including dyspnea as reported by participant or observed by investigator.
- Record participant's adherence to treatment program.
- Administer phone Tinnitus Functional Index (TFI) questionnaire.

7.2.3.5 Visit 7: Week 5 (Office Visit)

- Record vital signs and auscultate lungs.
- Review current medications and results of VAS log.
- Collect urine for electrolyte levels and urine osmolality. Perform urine pregnancy test, if applicable.
- Administer THI and Clinical Global Impression Improvement (CGI-I) questionnaires.
- Record adverse events as reported by participant or observed by investigator.
- Study drug reconciliation and record of participant's adherence to treatment program.
- Provide the study medication to the participant to use four times daily for the next 2 weeks.

7.2.3.6 Visit 8: Week 6 (Phone Visit)

• Review current medications.

- Assess and record adverse events including dyspnea as reported by participant or observed by investigator.
- Record participant's adherence to treatment program.
- Administer phone Tinnitus Functional Index (TFI) questionnaire.

7.2.3.7 Visit 9: Week 7 (Office Visit)

- Record vital signs and auscultate lungs.
- Review current medications and results of VAS log.
- Collect urine for electrolyte levels and urine osmolality. Perform urine pregnancy test, if applicable.
- Administer THI and Clinical Global Impression Improvement (CGI-I) questionnaires.
- Record adverse events as reported by participant or observed by investigator.
- Study drug reconciliation and record of participant's adherence to treatment program.
- Provide the study medication to the participant to use four times daily for the next 2 weeks.

7.2.3.8 Visit 10: Week 8 (Phone Visit)

- Review current medications.
- Assess and record adverse events including dyspnea as reported by participant or observed by investigator.
- Record participant's adherence to treatment program.
- Administer phone Tinnitus Functional Index (TFI) questionnaire.

7.2.3.9 Visit 11: Week 9 (Office Visit)

- Record vital signs and auscultate lungs.
- Review current medications and results of VAS log.
- Collect urine for electrolyte levels and urine osmolality. Perform urine pregnancy test, if applicable.
- Administer THI and CGI-I questionnaires.
- Record adverse events as reported by participant or observed by investigator.
- Study drug reconciliation and record of participant's adherence to treatment program.
- Randomize and dispense new study drug (active drug or placebo nasal spray) to use for the next 2 weeks.

7.2.3.10 Visit 12: Week 10 (Phone Visit)

- Review current medications.
- Assess and record adverse events including dyspnea as reported by participant or observed by investigator.
- Record participant's adherence to treatment program.
- Administer phone Tinnitus Functional Index (TFI) questionnaire.

7.2.3.11 Visit 13: Week 11 (Office Visit)

- Record vital signs and auscultate lungs.
- Review current medications and results of VAS log.
- Collect urine for electrolyte levels and urine osmolality. Perform urine pregnancy test, if applicable.
- Administer THI and CGI-I questionnaires.
- Record adverse events as reported by participant or observed by investigator.
- Record participant's adherence to treatment program.
- Provide the study medication to the participant to use four times daily for the next 2 weeks.

7.2.3.12 Visit 14: Week 12 (Phone Visit)

• Review current medications.

- Assess and record adverse events including dyspnea as reported by participant or observed by investigator.
- Record participant's adherence to treatment program.
- Administer phone Tinnitus Functional Index (TFI) questionnaire.

7.2.3.13 Visit 15: Week 13 (Office Visit)

- Record vital signs and auscultate lungs.
- Review current medications and results of VAS log.
- Collect urine for electrolyte levels and urine osmolality. Perform urine pregnancy test, if applicable.
- Administer THI and CGI-I questionnaires.
- Record adverse events as reported by participant or observed by investigator.
- Record participant's adherence to treatment program.
- Provide the study medication to the participant to use four times daily for the next 2 weeks.

7.2.3.14 Visit 16: Week 14 (Phone Visit)

- Review current medications.
- Assess and record adverse events including dyspnea as reported by participant or observed by investigator.
- Record participant's adherence to treatment program.
- Administer phone Tinnitus Functional Index (TFI) questionnaire.

7.2.4 Final Study Visit

Visit 17: Week 15 (Office Visit)

- Record vital signs and auscultate lungs.
- Review current medications and results of VAS log.
- Draw blood for CMP to be able to compare to baseline levels.
- Perform urine pregnancy test, if applicable.
- Administer THI and CGI-I questionnaires.
- Record adverse events as reported by participant or observed by investigator.
- Study drug reconciliation and record of participant's adherence to treatment program.

7.2.5 Withdrawal/Early Termination Visit

If the participant agrees, any participant who withdraws from the study or is terminated early, will be asked to come in for a final visit in which we will record vital signs, obtain blood for CMP, record adverse events, and review results of VAS, THI and CGI.

7.2.6 Unscheduled Visit

In the event of an unscheduled patient visit, the subject will undergo safety screening – a focused physical exam, and blood pressure, temperature, and heart rate documentation. Depending on the reason for the visit, the subject may be referred to the appropriate service for possible adverse event follow up. All adverse events reported by the subject or observed by the investigator will be documented and reported. Aside from adverse events, information gathered at these unscheduled visits will not be included in the statistical analysis.

7.3 Concomitant Medications, Treatments, and Procedures

All concomitant prescription medications taken during study participation will be recorded on the case report forms (CRFs). For this protocol, a prescription medication is defined as a medication that can be prescribed only by a properly authorized/licensed clinician. Medications to be reported in the CRF are concomitant prescription medications, over-the-counter medications and non-prescription medications. Review of concomitant medications will occur at every phone and office visit.

7.4 Prohibited Medications, Treatments, and Procedures

Current medications are reviewed at each visit. If at any point during the study, a participant begins taking dinoprostone or ephedrine, they must stop taking the prohibited medication in order to continue participating in the study.

7.5 Participant Access to Study Agent at Study Closure

At study end, participants will not be provided additional samples of study medication.

8 Assessment of Safety

8.1 Specification of Safety Parameters

8.1.1 Definition of Adverse Events (AE)

An *adverse event* (AE) is any symptom, sign, illness or experience that develops or worsens in severity during the course of the study. Intercurrent illnesses or injuries should be regarded as adverse events. Abnormal results of diagnostic procedures are considered to be adverse events if the abnormality:

- results in study withdrawal
- is associated with a serious adverse event
- is associated with clinical signs or symptoms
- · leads to additional treatment or to further diagnostic tests
- is considered by the investigator to be of clinical significance

8.1.2 Definition of Serious Adverse Events (SAE)

Serious Adverse Event

Adverse events are classified as serious or non-serious. A serious adverse event is any AE that is:

- fatal
- life-threatening
- requires or prolongs hospital stay
- results in persistent or significant disability or incapacity
- a congenital anomaly or birth defect
- an important medical event

Important medical events are those that may not be immediately life threatening, but are clearly of major clinical significance. They may jeopardize the subject, and may require intervention to prevent one of the other serious outcomes noted above. For example, drug overdose or abuse, a seizure that did not result in in-patient hospitalization, or intensive treatment of bronchospasm in an emergency department would typically be considered serious.

All adverse events that do not meet any of the criteria for serious should be regarded as *non-serious adverse events*.

8.1.3 Definition of Unanticipated Problems (UP)

Unanticipated Problems Involving Risk to Subjects or Others

Any incident, experience, or outcome that meets all of the following criteria:

- Unexpected in nature, severity, or frequency (i.e. not described in study-related documents such as the IRB-approved protocol or consent form, the investigators brochure, etc.)
- Related or possibly related to participation in the research (i.e. possibly related means there is a reasonable possibility that the incident experience, or outcome may have been caused by the procedures involved in the research)
- Suggests that the research places subjects or others at greater risk of harm (including physical, psychological, economic, or social harm).

8.2 Classification of an Adverse Event

8.2.1 Severity of Event

For AEs not included in the protocol defined grading system, the following guidelines will be used to describe severity.

- **Mild** Events require minimal or no treatment and do not interfere with the participant's daily activities.
- **Moderate** Events result in a low level of inconvenience or concern with the therapeutic measures. Moderate events may cause some interference with functioning.
- Severe Events interrupt a participant's usual daily activity and may require systemic drug therapy or other treatment. Severe events are usually potentially life-threatening or incapacitating.

8.2.2 Relationship to Study Agent

The clinician's assessment of an AE's relationship to study agent (drug, biologic, device) is part of the documentation process, but it is not a factor in determining what is or is not reported in the study. If there is any doubt as to whether a clinical observation is an AE, the event should be reported. All AEs must have their relationship to study agent assessed. In a clinical trial, the study product must always be suspect. To help assess, the following guidelines are used.

- **Related** The AE is known to occur with the study agent, there is a reasonable possibility that the study agent caused the AE, or there is a temporal relationship between the study agent and event. Reasonable possibility means that there is evidence to suggest a causal relationship between the study agent and the AE.
- Not Related There is not a reasonable possibility that the administration of the study agent caused the event, there is no temporal relationship between the study agent and event onset, or an alternate etiology has been established.

8.2.3 Expectedness

The PI will be responsible for determining whether an AE is expected or unexpected. An AE will be considered unexpected if the nature, severity, or frequency of the event is not consistent with the risk information previously described for the study agent.

8.3 Time Period and Frequency for Event Assessment and Follow-Up

The occurrence of an AE or SAE may come to the attention of study personnel during study visits and interviews of a study participant presenting for medical care, or upon review by a study monitor. All AEs including local and systemic reactions not meeting the criteria for SAEs will be captured on the appropriate RF. Information to be collected includes event description, time of onset, clinician's assessment of severity, relationship to study product (assessed only by those with the training and authority to make a diagnosis), and time of resolution/stabilization of the event. All AEs occurring while on study must be documented appropriately regardless of relationship. All AEs will be followed to adequate resolution.

Any medical condition that is present at the time that the participant is screened will be considered as baseline and not reported as an AE. However, if the study participant's condition deteriorates at any time during the study, it will be recorded as an AE. UPs will be recorded in the data collection system throughout the study.

Changes in the severity of an AE will be documented to allow an assessment of the duration of the event at each level of severity to be performed. AEs characterized as intermittent require documentation of onset and duration of each episode.

The PI will record all reportable events with start dates occurring any time after informed consent is obtained until 7 (for non-serious AEs) or 30 days (for SAEs) after the last day of study participation. At

each study visit, the investigator will inquire about the occurrence of AE/SAEs since the last visit. Events will be followed for outcome information until resolution or stabilization.

All unresolved adverse events should be followed by the investigator until the events are resolved, the subject is lost to follow-up, or the adverse event is otherwise explained. At the last scheduled visit, the investigator should instruct each subject to report any subsequent event(s) that the subject, or the subject's personal physician, believes might reasonably be related to participation in this study. The investigator should notify the study sponsor of any death or adverse event occurring at any time after a subject has discontinued or terminated study participation that may reasonably be related to this study. The sponsor should also be notified if the investigator should become aware of the development of cancer or of a congenital anomaly in a subsequently conceived offspring of a subject that has participated in this study.

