5.7.2 Handling of Participant Withdrawals or Termination

Subjects may withdraw from the study at any time. Subjects that choose to withdraw early from the study will be voluntarily surveyed for reasons for withdrawal. They will be asked for permission to continue to utilize the data collected up to the point of withdrawal for research purposes. Should they decline, all data past the note of withdrawal will be deleted from the record system. Subjects will be required to return any unused samples of nasal spray.

We will reach out to those withdrawn or terminated participants or those who discontinue the study agent but remain in the study for follow-up via 3 phone calls to them. Should participants not respond to our phone calls, a certified letter will be sent to their home address. For those participants who withdrew because of AEs, we will try to continuously follow them until AEs resolve.

We plan to replace participants who withdraw or discontinue the study early, in order to collect the minimum data required to determine the efficacy of the study drug, per Section 9.3 of the Statistical Considerations for the study, Analysis Datasets.

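### For completers, nothing is scheduled to support the 7-day AE and 30-day SAE window after participation, and the last-visit instruction asks for later events believed related rather than all of them

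*Combined protocol and SAP*

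**What the plan says.** Section 8.3 sets the recording period: "The PI will record all reportable events with start dates occurring any time after informed consent is obtained" and "until 7 (for non-serious AEs) or 30 days (for SAEs) after the last day of study participation". The term *reportable* is not defined there. Active questioning is tied to visits: at "each study visit, the investigator will inquire about the occurrence of AE/SAEs since the last visit". The same section also recognises events that surface through "interviews of a study participant presenting for medical care, or upon review by a study monitor".

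The visit table in Section 7.1.1, the visit description in Section 7.2.4 and the Schedule of Events in Section 18 all end at Visit 17, Week 15. Section 5.5 counts about 17 visits in total.

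For the time after the last visit, Section 8.3 tells the investigator to ask each subject to report later events that the subject or the subject's own physician "believes might reasonably be related to participation in this study". The investigator's duty to notify the sponsor of later events carries a similar limit. Events still open are followed to an outcome.

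On causality, Section 8.2.2 says the clinician's assessment of relationship is documented, "but it is not a factor in determining what is or is not reported in the study". Section 8.4.1 requires IRB reporting of adverse events that are unexpected, related and harmful. Section 8.4.2 requires it for all serious adverse events, with no condition on cause.

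For people who leave early, Section 5.7.2 states "We will reach out to those withdrawn or terminated participants", with three phone calls and then a certified letter if there is no reply.

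**The concern.** The protocol promises a recording window beyond the last visit but schedules nothing to fill it for completers. What it does provide is a request that leaves the first causality judgement to the participant or an outside physician, before any study clinician hears of the event. An event judged unrelated at that stage, such as a hospital admission in week 3 after Visit 17, falls inside the 30-day window and would be reportable under Section 8.4.2 once discovered. Yet no step in the plan asks for it. At stake is whether the trial can say that it observed participants for serious events over the period it names. A reader of the safety results would take the 7-day and 30-day figures as a description of follow-up actually carried out.

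**Working it through.** No sample size, power or event count is involved. The check is a count of contacts and a comparison of sections.

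**1. Contacts available to a completer.** I take the last day of study participation to be Visit 17. The protocol does not define it, but no later day exists in the schedule.

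| Source | Last entry | Contacts in the next 7 days | Contacts in the next 30 days |
|---|---|---|---|
| 7.1.1 visit table | Week 15 | 0 | 0 |
| 7.2.4 Final Study Visit | Visit 17 | 0 | 0 |
| 18 Schedule of Events | Visit 17 | 0 | 0 |

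Up to that point contacts are about weekly, with office visits and phone calls alternating. Active inquiry therefore goes from weekly to none on the day the window opens.

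**2. Routes that remain for a new-onset event after Visit 17.**
- Spontaneous report under the last-visit instruction, limited to events believed related by the subject or personal physician.
- Presentation for medical care, or monitor review (8.3). Both are passive.
- An unscheduled visit (7.2.6), where adverse events are documented. This also depends on the participant coming forward.

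Follow-up of unresolved events (8.3) does not help here, because it concerns events already known.

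**3. What the window should contain, against what is asked for.** Because *reportable* is undefined, I tried two readings.

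| Event type | Window | Narrow reading (IRB reporting rules in 8.4) | Broad reading (all AEs) | What the participant is asked to report |
|---|---|---|---|---|
| Non-serious AE | 7 days | Unexpected, related and harmful: largely matches the instruction | All: the instruction is narrower | Believed related |
| SAE | 30 days | All SAEs: the instruction is narrower | All SAEs: the instruction is narrower | Believed related |

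The gap for serious events appears under both readings. The gap for non-serious events appears only under the broad one.

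**4. Comparison with 8.2.2.** That section keeps relatedness out of the decision on what is reported. The last-visit instruction makes believed relatedness the condition for telling the site at all. Section 8.3 also reserves the relationship judgement for people trained and authorised to diagnose. A participant deciding alone whether to call is not in that group.

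**5. Size.** The documents give no event rate after treatment and no capture rate for passive reports, so the share of events missed cannot be calculated.

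**The case against.** Several objections have weight.

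- **The window is not without capture.** A reader might infer that almost nothing would be recorded after Visit 17. The documents do not support that: passive routes exist, the personal physician can also prompt a report, open events are followed, and no figure shows how much would be lost. What stands is that capture is passive and the explicit request is filtered.
- **The conflict with 8.2.2 is one of principle.** Its wording concerns the clinician's assessment, not what a former participant volunteers. The statement in 8.3 that events are documented whatever their relationship covers events while on study. Neither clearly governs the later period. This weakens the point for non-serious events and leaves the conflict with 8.4.2 for serious ones.
- **The instruction has no time limit and is not named as the mechanism for the window.** True, but the plan names no other mechanism specific to completers.
- **No bias between arms follows.** One could note that participants switched to placebo at Visit 11 have six contacts after stopping oxytocin (Visits 12 to 17), while those kept on oxytocin have none, and infer unequal ascertainment by arm. That pattern comes from the randomised-withdrawal design. Both arms have the same visits, the same Visit 17 and the same instruction, and nothing says that later events enter the by-arm tables in 9.4.3 and 9.4.4.
- **Nor does better capture in early leavers.** The calls in 5.7.2 have no stated timing, and following adverse events is explicit only for those who withdrew because of them.
- **The consequence is likely small.** Section 2.1 gives a half-life of 3-17 minutes, Section 2.4.1.1 expects adverse events to be short-lived, and Visit 17 includes adverse event review, vital signs, lung auscultation and a metabolic panel. This stands and sets the severity. It does not remove the commitment that 8.3 makes.

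**Conclusion.** The point holds as a minor one. For completers, the stated window has 0 scheduled contacts in either 7 or 30 days, and new-onset events are captured passively, with a direct request only for those believed related. The mismatch is firm for serious events, since it appears whichever way *reportable* is read. For non-serious events it depends on that undefined term. The conclusion assumes that a completer's last day of participation is Visit 17 and that the design schematic, which could not be seen, adds no later contact. It makes no claim about the number of missed events, about bias between arms, or about a difference between completers and those who leave early.

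**What to change.** 1. **Reword the last-visit instruction in 8.3.** Ask participants to report every serious event within 30 days, and every new or worsened event within 7 days, of the last day of study participation, whatever they think caused it. After that, ask for events believed related, as now. In the same edit, say what *reportable* and *last day of study participation* mean. Cost: wording only.
2. **Add a short closing phone contact** to 7.2.4 and the Schedule of Events at day 30 after the last day of study participation, so that it uses the same anchor as the window. The adverse event questions from the existing phone visits will serve. A call at day 30 that asks about everything since Visit 17 covers both windows; a second call at day 7 is optional and would help recall of non-serious events. Cost: for 30 completers, 30 x 1 = 30 calls, or 30 x 2 = 60 with the optional one, by staff who already phone participants every second week.
3. **List events starting after Visit 17 separately** from on-treatment events in the outputs under 9.4.3 and 9.4.4. Cost: one short listing.
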